#### 9.1.1.3 Selection of the RP2D

The RP2D of E7766 will be selected based on an integrated evaluation of safety, tolerability, clinical activity, PK data, and any available pharmacodynamics data for all dose levels or all available data according to the following guidelines:

Eisai Confidential Page 55 of 138

- The RP2D must not exceed the MTD, as defined in the Dose Escalation part of the study.
- Consideration will be given to other toxicities including: AEs assessed as related to study drug treatment but not considered dose limiting, late immune-related toxicities (up to 90 days after last dose of the study drug), the nature and frequency of toxicities, and the emergence of any specific category of toxicities.
- Consideration will be given to the tumor response(s) and antitumor activity.
- Pharmacodynamic demonstration of biologic activity, including but not limited to: activation of STING-mediated immune pathways and modulation of innate and adaptive immune response in the tumors and/or in the peripheral blood such as INFβ, CXCL10, and MCP1.

The investigators and sponsors will together conduct the evaluation and the recommended Phase 2 dose/doses and/or any modification to the dosing regimen will be agreed upon jointly.

## 9.1.2 Dose Expansion

Expansion arms shall be opened in specific tumor types and populations with treatment at the E7766 RP2D.

Safety and clinical activity of E7766 at the RP2D will be tested in separate expansion arms with defined populations potentially including but not limited to melanoma, HNSCC, breast cancer, colorectal cancer, and/or other tumors. About 40 patients will be recruited in each expansion arm.

Eisai Confidential Page 56 of 138

## 9.1.3 Study Phases

There will be 4 phases for each subject in the Dose Escalation part and the Dose Expansion, part: a Pretreatment Phase, a Treatment Phase, an Extension Phase, and a Follow-Up Phase.

Phase	Pretreatment	Treatment	Extension	Follow-Up
Period	Screening  Day -28 to Day -1  Baseline  Day -3 to  Day -1	For Dose Expansion part, Treatment Phase is 6 cycles (one Induction cycle + 5 Maintenance cycles  E7766 administ 8, 15 and Cycle	Maintenance Cycles Treatment continuation until  Confirmed disease progression Disappearance or nonavailability of any injectable lesions Unacceptable toxicity Subject request Withdrawal of consent Termination of the study by the Sponsor Pregnancy Investigator decision  ration: Cycle 1 on Days 1, 2 onwards every 3 weeks in Day 1 only	Follow-up every 12 weeks ± 1 week for OS for up to 2 years or until subject is deceased, or until the completion of the primary analysis, whichever is earlier, or if the sponsor terminates the study

## Figure 4 Study Phases

#### 9.1.3.1 Pretreatment Phase

This phase will last no longer than 28 days and includes:

- A Screening Period spanning Day -28 to Day -1 to obtain informed consent and
  establish protocol eligibility. Informed consent will be obtained after the study has been
  fully explained to each subject and before the conduct of any screening procedures or
  assessments. Procedures to be followed when obtaining informed consent are detailed
  in Section 5.3.
- A Baseline Period from Day -3 to Day -1 to establish disease characteristics before treatment

#### 9.1.3.2 Treatment Phase

Subjects whose screening assessments and evaluations are completed and reviewed by the principal investigator and who continue to meet all of the inclusion/exclusion criteria will enter the Treatment Phase.

Eisai Confidential Page 57 of 138

The Treatment Phase will extend from the start of study drug administration in Cycle 1 and will last for 1 treatment cycle of 21 days in the Dose Escalation part and 6 cycles in the Dose Expansion part. At the end of the Treatment Phase subjects will continue to the Extension Phase.

#### 9.1.3.3 Extension Phase

In the Extension Phase, subjects who are receiving study drug at the end of the Treatment Phase will continue to receive drug treatment at the same dose and according to the Dosing Schedule described in Section 9.4.1.1.

In the **Treatment** and **Extension phases**, subjects will undergo disease assessments every 6 weeks in the case of solid tumors and 12 weeks in the case of lymphomas, and will discontinue study drug at the time of confirmed disease progression (per iRECIST or LYRIC), disappearance or nonavailability of any injectable lesions, development of unacceptable toxicity, subject request, withdrawal of consent, termination of the study program, pregnancy, or investigator decision.

An off-treatment assessment should occur within 30 days after the final dose of study treatment.

Subjects who are continuing to derive clinical benefit in the view of the investigator at the time of study termination by the sponsor, can continue to be treated with E7766 after discussion with the sponsors.

### 9.1.3.4 Follow-Up Phase

The Follow-Up Phase will begin immediately after the off-treatment assessments have been completed and will continue for up to 2 years or until study subject is deceased, or until the completion of the primary analysis, whichever is earlier, unless the subject withdraws consent or until the sponsor terminates the study.

Subjects who discontinue study treatment before disease progression will continue to undergo disease assessment every 6 weeks in case of solid tumors and 12 weeks in case of lymphomas until documentation of disease progression or start of another anticancer therapy.

Subjects will be followed every 12 weeks ( $\pm 1$  week) for survival, performance status and subsequent anticancer treatments. The sponsor may decide to terminate survival follow-up anytime during the Extension Phase or when all subjects have discontinued study treatment. Survival follow-up will be conducted in person or via phone call.

In the Follow-Up Phase, subjects will be treated by the investigator according to the prevailing local standard of care.

Eisai Confidential Page 58 of 138

[figure not shown]
The sponsor may decide to terminate survival follow-up anytime during the Extension Phase or when all subjects have discontinued study treatment.

# 9.2 Discussion of Study Design, Including Choice of Control Groups

In this FIH study (intratumoral route), E7766 will be studied to assess safety and tolerability, clinical activity, PK, and to explore pharmacodynamics markers to identify potential human-relevant biomarkers of safety and efficacy. The study will identify an MTD and/or a RP2D of E7766. Phase 1b expansion arms in selected tumor types are planned after RP2D has been determined.

E7766 will be tested in sequential escalating dose cohorts (n=2) using the mTPI method. Expanding individual dose levels to generate additional safety, drug administration-related, biomarker, and/or PK information will be allowed.

#### Starting Dose Determination and Subsequent Dose Escalation and Descalation

[figure not shown]

Eisai Confidential Page 59 of 138

E7766 will be administered intratumorally on Days 1, 8, and 15 in the first cycle, and then on Day 1 of each subsequent cycle every 3 weeks. Treatment is planned until progressive disease or until other discontinuation criteria have been met.

The escalation steps and doses of subsequent dose groups will be determined based on the E7766-related AEs that develop in subjects in the prior dose group during Cycle 1 as per improved mTPI methodology as outlined in Section 9.7.4.1. In addition, intermediate doses can be further added if necessary based on the safety or PK of the previously tested dose. The addition of new dose levels will be decided based on discussions between the investigators and sponsors.

## Translational approach

# 9.3 Selection of Study Population

Approximately 35 to 40 subjects will be enrolled in the Dose Escalation part and 80 subjects will be enrolled in the Dose Expansion part. Subjects who do not meet all of the inclusion criteria or who meet any of the exclusion criteria will not be eligible to receive study drug.

#### 9.3.1 Inclusion Criteria

Subjects must meet all of the following criteria to be included in this study:

- 1. Age  $\geq$  18 years.
- 2. Eastern Cooperative Oncology Group (ECOG) Performance Status of 0 or 1.

Eisai Confidential Page 60 of 138

- 3. Life expectancy  $\geq 12$  weeks.
- 4. Subjects with solid tumors or lymphomas, confirmed by available histopathology records or current biopsy, that are advanced, nonresectable, or recurrent and progressing since last antitumor therapy, and for which no alternative standard therapy exists.
- 5. Subjects must have a minimum of one injectable lesion which is also accessible for biopsy, and if available, one other measurable lesion also accessible for biopsy. An injectable lesion is defined as being measureable (defined below) with a maximum of 3.0 cm longest diameter, accessible for injection as judged by the investigator, and has not been subjected to any prior intratumoral treatment or radiotherapy. Lesions selected for injection must not be too close to a major vessel, as judged by the investigator, and not be associated with increased risk of bleeding, eg, subcapsular liver lesions or hypervascular tumors.

#### Measurable lesions are:

- a. Solid tumors: At least 1 lesion of ≥1 cm by longest axial diameter or ≥1.5 cm short axis diameter if a nodal lesion, which is serially measurable according to modified RECIST 1.1 using CT/MRI or photography. Lesions that have had external beam radiotherapy or locoregional therapies such as radiofrequency ablation must show evidence of progression to be deemed a target lesion (Appendix 1, Appendix 2).
- b. Lymphoma: At least 1 lymph node with a longest diameter >1.5 cm or an extranodal lesion with a longest diameter >1.0 cm (Appendix 3).
- 6. Prior anticancer therapy such as chemotherapy, immunotherapy (eg, tumor vaccine, cytokine, checkpoint inhibitors), or investigational drugs, or any vaccine must have been completed at least 4 weeks before study drug administration, and all AEs must have either returned to baseline or stabilized. Subjects with prior immunotherapy known to have experienced severe nontolerable toxicities attributed to drug should be excluded.
- 7. Prior definitive radiation therapy must have been completed at least 6 weeks and prior palliative radiotherapy at least 2 weeks before study drug administration.

  Radiopharmaceuticals (eg, strontium, samarium) must be at least 8 weeks before study drug administration.
- 8. Immunosuppressive doses of systemic medications, such as steroids or absorbed topical steroids (doses >10 mg/day prednisone or equivalent) must have been discontinued at least 4 weeks before study drug administration.
- 9. Subjects with prior Hepatitis B or C are eligible if they have adequate liver function as defined by Inclusion Criterion #13.
- 10. Left ventricular ejection fraction (LVEF) >50% or within normal limits per institutional practice, on echocardiography or multigated acquisition (MUGA) scan.
- 11. Adequate renal function defined as serum creatinine <1.5 × ULN (or use SI units or calculated creatinine clearance ≥50 mL/min per the Cockcroft and Gault formula [Appendix 4]).

Eisai Confidential Page 61 of 138

- 12. Adequate bone marrow function:
  - a. Absolute neutrophil count (ANC)  $\geq 1000/\text{mm}^3$  ( $\geq 1.0 \times 10^3/\mu\text{L}$ )
  - b. Platelets  $\ge 75,000/\text{mm}^3 (\ge 75 \times 10^9/\text{L})$
  - c. Hemoglobin ≥9.0 g/dL
- 13. Adequate liver function defined by:
  - a. Adequate blood coagulation function as evidenced by an International Normalized Ratio (INR)  $\leq$  1.5
  - b. Total bilirubin ≤1.5 × ULN except for unconjugated hyperbilirubinemia or Gilbert's syndrome
  - c. Alkaline phosphatase (ALP), ALT, and AST ≤3 × ULN (in the case of liver metastasis ≤5 × ULN) unless there are bone metastases. Subjects with ALP values >3 × ULN and known to have bone metastases can be included.
- 14. Willing and able to comply with all aspects of the protocol.
- 15. Provide written informed consent prior to any study-specific screening procedures.

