  - b. Total bilirubin  $\leq$  1.5  $\times$  ULN except for unconjugated hyperbilirubinemia or Gilbert's syndrome
  - c. Alkaline phosphatase (ALP), ALT, and AST  $\leq 3 \times \text{ULN}$  (in the case of liver metastasis  $\leq 5 \times \text{ULN}$ ) unless there are bone metastases. Subjects with ALP values  $> 3 \times \text{ULN}$  and known to have bone metastases can be included.
- 14. Willing and able to comply with all aspects of the protocol.
- 15. Provide written informed consent prior to any study-specific screening procedures.

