#### 9.3.2 Exclusion Criteria

Subjects with any of the following criteria will be excluded from this study:

- 1. Other malignancy active within the previous 2 years except for basal or squamous cell skin cancer, superficial bladder cancer, or carcinoma in situ of the cervix or breast that has completed curative therapy.
- 2. Subjects with any active autoimmune disease (Appendix 5) or a documented history of autoimmune disease, except for subjects with vitiligo or resolved childhood asthma/atopy.
- 3. Known human immunodeficiency virus (HIV) infection.
- 4. Active infection requiring therapy, including known positive tests for Hepatitis B surface antigen or Hepatitis C ribonucleic acid (RNA).
- 5. Major surgery within 4 weeks before the first dose of study drug.
- 6. Concurrent medical condition requiring the use of immunosuppressive medications or immunosuppressive doses of systemic medications, such as steroids or absorbed topical steroids (doses >10 mg/day prednisone or equivalent).
- 7. Brain metastases that are untreated or in the posterior fossa or involve the meninges. Subjects with stable or progressing brain metastases (except in the posterior fossa or involving the meninges) previously treated with brain stereotactic radiotherapy (SRT), whole-brain radiotherapy (WBRT) and/or surgery are allowed as long as the subject is asymptomatic neurologically and does not require immediate local intervention (radiotherapy and/or surgery). In addition, subjects must be off immunosuppressive doses of systemic steroids (>10 mg/day prednisone or equivalent) for at least 4 weeks before study drug administration.
- 8. Prolongation of corrected QT (QTcF) interval to >450 msec for males and females, when electrolytes balance is normal.

Eisai Confidential Page 62 of 138

- 9. Significant cardiovascular impairment: history of congestive heart failure greater than New York Heart Association (NYHA) Class II, uncontrolled arterial hypertension, unstable angina, myocardial infarction, or stroke within 6 months of the first dose of study drug, or cardiac arrhythmia requiring medical treatment (including oral anticoagulation).
- 10. Subjects on oral anticoagulants including low dose aspirin. To meet eligibility, these subjects can be switched to receive preventive dose of low molecular weight heparin (LMWH). It is recommended that their LMWH treatment is stopped 24 hours before the intratumoral injection and resumed again 24 hours after the injection.

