- 11. Any history of a medical condition or a concomitant medical condition that, in the opinion of the investigator, would compromise the subject's ability to safely complete the study.
- 12. Females who are breastfeeding or pregnant at Screening or Baseline (as documented by a positive beta-human chorionic gonadotropin [β-hCG] (or human chorionic gonadotropin [hCG]) test with a minimum sensitivity of 25 IU/L or equivalent units of β-hCG [or hCG]). A separate baseline assessment is required if a negative screening pregnancy test was obtained more than 72 hours before the first dose of study drug.
- 13. Females of childbearing potential must not have had unprotected sexual intercourse within 30 days before study entry and must agree to use a highly effective method of contraception (total abstinence [if it is their preferred and usual lifestyle], a contraceptive implant, an oral contraceptive, or have a vasectomized partner with confirmed azoospermia) throughout the entire study period and for 180 days after study drug discontinuation. For sites outside of the EU, it is permissible that if a highly effective method of contraception is not appropriate or acceptable to the subject, then the subject must agree to use a medically acceptable method of contraception, ie, double barrier methods of contraception such as condom plus diaphragm or cervical/vault cap with spermicide. If currently abstinent, the subject must agree to use a highly effective method as described above if she becomes sexually active during the study period or for 180 days after study drug discontinuation. Females who are using hormonal contraceptives must have been on a stable dose of the same hormonal contraceptive product for at least 28 days before dosing and must continue to use the same contraceptive during the study and for 180 days after study drug discontinuation.

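### Inclusion 13c, read literally, removes the ALT and AST entry limits for any subject with bone metastases, although an ALP-only exception was probably meant

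*Protocol*

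**What the plan says.** Criterion 13 defines the liver function needed for entry. Part (a) covers coagulation ("Adequate blood coagulation function as evidenced by an International Normalized Ratio (INR") with a ceiling of 1.5. Part (b) covers bilirubin ("Total bilirubin ≤1.5 × ULN except for unconjugated hyperbilirubinemia"). Part (c) covers the enzymes and has two sentences:

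- First: "Alkaline phosphatase (ALP), ALT, and AST ≤3 × ULN (in the case of liver metastasis ≤5 × ULN) unless there are bone metastases".
- Second: "Subjects with ALP values >3 × ULN and known to have bone metastases can be included".

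The synopsis carries the same pair of sentences, with the same join between them: "unless there are bone metastases. Subjects with ALP values". The SAP does not restate the eligibility criteria. Inclusion Criterion 9 depends on criterion 13, because it admits subjects with past hepatitis B or C provided that criterion 13 is met.

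**The concern.** The first sentence of 13c groups ALP, ALT and AST under one limit and closes with one exception. Nothing in that sentence confines the exception to ALP. The liver-metastasis allowance in the same sentence plainly covers all three analytes, so a reader has grammatical grounds to treat the bone-metastasis clause the same way.

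The criterion therefore supports two different entry rules for ALT and AST. One site could dose a subject with bone metastases and markedly raised transaminases while another excludes the same subject. The study is first-in-human by the intratumoral route, and escalation starts with cohorts of two. The affected group is foreseeable: the protocol requires screening bone scans in tumor types where bone metastases are common, and breast cancer is a named candidate for expansion.

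**Working it through.** No calculation in the plan bears on this point, so the check is of wording and coverage.

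**Step 1. The two readings of 13c for a subject with bone metastases.**

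| | First sentence taken literally | ALP-only, as the second sentence suggests |
|---|---|---|
| ALP | no limit | no limit |
| ALT, AST, no liver metastases | no limit | ≤3×ULN |
| ALT, AST, with liver metastases | no limit | ≤5×ULN |

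The readings part for subjects with bone metastases whose ALT or AST exceeds 3×ULN, or 5×ULN if they also have liver metastases.

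**Step 2. Does the second sentence settle it?** It says who may enter with high ALP. It neither mentions ALT or AST nor says that their limits still apply. It is evidence of intent, not a restored ceiling.

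**Step 3. Does another criterion supply the missing limit?** Sections 9.3.1 and 9.3.2 list 15 inclusion and 17 exclusion criteria, 15 + 17 = 32. Only 13c gives an ALT or AST value. The provisions nearest to a substitute are:

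- 13a and 13b: INR and total bilirubin only.
- Exclusion 4: "Active infection requiring therapy, including known positive tests for Hepatitis B surface antigen or Hepatitis C ribonucleic acid (RNA". This addresses infection, not enzyme level.
- Exclusion 11: a past or "concomitant medical condition that, in the opinion of the investigator, would compromise" the subject's safe completion of the study. This is judgement, with no value.
- Section 9.1.3.2: screening results are "reviewed by the principal investigator and who continue to meet all of the inclusion/exclusion criteria". The review applies the same criteria, so it inherits the ambiguity.
- Section 9.5.1.5.3: chemistry is reviewed before dosing, with reference to Table 4. That table governs E7766-related toxicity, not entry.

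None sets an ALT or AST entry limit.

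**Step 4. An illustrative subject.** Assume bone but not liver metastases, ALT 6×ULN, normal INR and normal bilirubin. The ALT value is my choice for illustration.

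- ALP-only reading: 6/3 = 2.0 times the limit, so ineligible.
- Literal reading: no ALT limit applies. The subject meets 13a, 13b and 13c, and would at any ALT level.

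**Step 5. How the DLT rules treat such a subject (Section 9.1.1.2).** The Grade 3-or-higher laboratory rule applies only if the finding was Grade 1 or lower at baseline. The rule at >8×ULN, or >5×ULN for 14 days or more, is written for hepatic metastases. The rule for raised baseline enzymes also requires raised bilirubin. The general clauses (clinically significant toxicity of Grade 3 or above, investigator and medical monitor opinion, delayed Cycle 2) remain available but rest largely on judgement. In a cohort of two, a single DLT moves the Table 1 decision from escalate to de-escalate.

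**The case against.** The strongest reply is that the two sentences form one criterion. If the first already waived all three analytes, the second would be redundant; it has work to do only if it identifies ALP as the exempt analyte. The broad reading also defeats the purpose of a liver-function criterion: it would cap transaminases at 5×ULN in subjects with liver metastases yet leave them uncapped because of disease in bone. Most investigators would probably infer the ALP-only intent, and Exclusion 11 lets them refuse a subject whose raised transaminases are unexplained.

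There are further protections during treatment: at least 30 hours in clinic after the first escalation-part dose, chemistry at 6 and 24 hours after that dose and before the Day 8 and Day 15 doses, and the general DLT clauses. Finally, escalation ended early without an MTD (SAP Section 7) and no expansion subjects will be enrolled (SAP Section 3.2.2), so little or no future enrolment in this study would change.

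Much of this stands. ALP-only is the likelier intent, and the practical urgency is low. But likely intent does not make the text unambiguous, Exclusion 11 does not make sites consistent, and the monitoring and DLT provisions act after a subject has been dosed. They do not replace an entry limit.

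**Conclusion.** The concern holds as a wording defect in a safety threshold. Followed literally, 13c admits subjects with bone metastases at any ALT or AST level, and no other eligibility criterion gives a value that would stop them. The gap extends to subjects with past hepatitis B or C and bone metastases, because Inclusion 9 relies on criterion 13, though Exclusion 4 still removes those with known positive tests.

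The size in numbers of subjects cannot be given: the documents do not report how many have bone metastases with raised ALT or AST, and nothing shows that any site used the broad reading. No estimate is affected, since no MTD was determined and the expansion part will not be analysed. The conclusion rests on the text of the criterion, which is identical in substance in the synopsis and Section 9.3.1, and needs no assumption about the data. It should be corrected, particularly before the wording is reused.

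**What to change.** Reword 13c in both the synopsis and Section 9.3.1, for example:

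> ALT and AST ≤3×ULN (≤5×ULN with liver metastases). ALP ≤3×ULN (≤5×ULN with liver metastases), except that ALP above these limits is allowed with known bone metastases.

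This keeps both liver-metastasis allowances and the ALP exception, and gives ALT and AST one limit that bone metastases do not lift.

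The cost is one sentence in two places. No other criterion, DLT rule or analysis changes. If sites already apply the ALP-only reading, nobody loses eligibility. If any apply the broad reading, subjects with bone metastases and ALT or AST above the limits would no longer qualify; their number is not known from the documents.
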